3.3 Inclusion of Women and Minorities

Both men and women of all races and ethnic groups are eligible for this trial.

4 Enrollment Plan/ Patient Registration and Randomization

4.1 Registration and Randomization

Eligible patients will be entered on study at UCSF by the Study Coordinators. All patients who sign the informed consent document will be registered in OnCore and the Brain Tumor Research Center Tissue Bank database.

Arm 1: Patients will receive IMA950- poly-ICLC vaccine plus varlilumab. **Arm 2**: Patients will receive IMA950- poly-ICLC vaccine alone.

The study is designed with a staggered safety lead-in with the first 3 patients assigned to Arm 2. The first 3 patients of the study will be enrolled in Arm 2 in a staggered manner as follows. After the first patient of the study is enrolled in Arm 2, Patient number 2 and 3 will not be enrolled until the previous patient receives 4 pre-surgery vaccines and recover from clinically indicated surgery for at least 6 weeks after surgery without a regimen-limiting toxicity (RLT) to confirm the safety of IMA950-poly-ICLC vaccine.

If any of the first 3 patients on Arm 2 shows a RLT (see definition in section 5.3), an additional 3 patients (patients 4, 5 and 6) will be enrolled in the same, staggered manner in Arm 2 while Arm 1 enrollment is held. If 2 or more of the patients on Arm 2 show a RLT, the arm will be considered intolerable and the study will be closed. If only one total of the 6 patients shows an RLT in Arm 2, the randomized design will be cancelled and the study will proceed with Arm 2 only to primarily evaluate the safety of the Arm 2 regimen. When the study is completed with the total evaluable 15 patients in Arm 2, we will review the safety data, and discuss with the FDA and IRB regarding the extension of the study to Arm 1.

If none of the first 3 patients treated on Arm 2 demonstrates a RLT, then 3 further patients will be enrolled in Arm 1 (with varlilumab) in the same staggered manner (subsequent patients will not be enrolled until the respective previous patient receives 4 pre-surgery vaccines and recover from clinically indicated surgery for at least 6 weeks after surgery without an RLT to confirm the safety of IMA950-poly-ICLC-varli treatment. If one of first 3 patients on Arm 1 shows a **Regimen Limiting Toxicity** an additional 3 patients will be enrolled in the same, staggered manner in Arm 1. If 2 or more of the patients on Arm 1 show a RLT, the arm will be considered intolerable.

12 April 2020 Page 27 of 88 confidential

If Arm 2 is tolerable but Arm 1 is not, then, the study will be carried out with Arm 2 only.

If both arms are found tolerable, then subsequent patients will then be randomized into one of the two arms for the pre-surgical part of the study. **Arm 1**: Patients will receive IMA950-poly-ICLC vaccine plus varlilumab. **Arm 2**: Patients will receive IMA950-poly-ICLC vaccine alone. The randomization will take place in a 1:1 ratio between the two arms with the stratification based on whether the patient is newly diagnosed vs. recurrent.

Patients will be assigned to treatment by means of the UCSF Biostatistics Facility randomization system in an open label fashion. Information on the two arms will be loaded into the database and the treatment arm assigned to the subjects when the subject's initials and ID# are entered into the program. Results of randomization will not be blinded, and no placebo will be used.

4.2 Patients Who Are Registered and Do Not Receive Study Treatment

If a patient is registered to the study and is later found not able to begin study treatment, for whatever reason, the patient will be removed from study and treated at the physician's discretion. Such a patient will be replaced to complete the enrollment. If a patient receives any study therapy and then is discontinued for whatever reason, study staff will update the database for the patient's non-treatment status. Study data will be collected until the time the patient is taken off study. The reason for removal from study will be clearly indicated in the data base. The removed patient must be followed according to Section 5.2.8.

4.3 Replacement

Patients who receive at least 4 post-surgery vaccines will not be replaced because their PBMC on week 13 would allow for the primary endpoint evaluation. Subjects who are considered non-evaluable for the immunological endpoint will be replaced but still evaluated for the primary endpoint of safety and the secondary endpoint of efficacy. Evaluable patients for the immunological primary endpoint are study-eligible patients who receive at least four post-surgery vaccines. If the pathological diagnosis upon the resected tissue indicates WHO III or IV grade tumors, those patients will be ineligible for post-surgery courses and replaced.

5 Treatment Plan

5.1 Drug Information

5.1.1 IMA950

The drug product IMA950 comprises a mixture of 12 individual drug substances (peptides). IMA950 also contains Mannitol and Poloxamer 188 (Lutrol F68) as excipients in the formulation. Eleven of these peptides are TUMAPs derived from target proteins relevant in GBM. They include 9 HLA-A*02 class I binding peptides with the capacity to activate CTLs, one elongated class I-binding peptide, and one HLA class II-binding peptide with the capacity to activate helper T cells. In addition, IMA950 contains one HLA class I-binding

12 April 2020 Page 28 of 88 confidential

marker peptide from Hepatitis B virus core antigen with known immunogenicity. The lyophilisate, including peptides and excipients, is a white powder.

Storage conditions

IMA950 lyophilized powder for solution for injection should be stored at -20°C.

Shipment conditions

IMA950 lyophilized powder for solution for injection should be shipped at a temperature below -15°C. Upon receipt at clinical sites, IMA950 should be stored at -20°C.

Temperature excursions during transport, shipment and storage

Based on the good stability data at -20°C, +5°C, +25°C and +40°C it is justified to accept short term temperature excursions during transport, shipment and storage of IMA950 at clinical sites up to +25°C for a maximum of up 72 hours. It is not expected that a temperature excursion as defined above will have any influence on the quality of IMA950.

5.1.2 Poly-ICLC (Hiltonol)

Poly-ICLC is classified as an investigational new drug. It is a synthetic complex of polyinosinic and polycytidylic acid, stabilized with polylysine and carboxymethyl cellulose. The thermal denaturation point is 89.5°C, about 40°C above that of plain polyl.polyC; the resistance to hydrolysis is several times that of the parent compound, and it induces peak levels of about 1000-2000 IU of interferon- α per mL of serum in monkeys given 1 mg/kg intravenously.

Availability of Poly-ICLC

Poly-ICLC is available from Oncovir, Inc.							
Contact:							

Storage & Stability of Poly-ICLC

Poly-ICLC is supplied in vials each containing 1cc of translucent solution with a concentration of 2 mg per cc. It is stable at room temperature for several days, but is better stored refrigerated at about 40°F (not frozen).

5.1.3 Varlilumab

12 April 2020 Page 29 of 88 confidential

Description, Packaging and Labeling

Detailed technical information regarding varillumab can be found in the Investigator's Brochure. Varillumab is a recombinant, fully human mAb of the IgG1k isotype that specifically binds human CD27.

Varlilumab Drug Product is formulated as a clear, colorless, sterile solution intended for single-use parenteral administration. Varlilumab is provided in vials containing a nominal volume of 10.0 ml of a buffered solution composed of 5.0 mg/mL varlilumab protein, Sodium Phosphate, Potassium Phosphate, Potassium Chloride, Sodium Chloride, and Polysorbate 80 with a pH of 7.0.

Varlilumab will be labeled according to the requirements of local law and legislation. A copy of label text will be made available to study sites upon request.

Storage and Handling for Varlilumab

Varlilumab drug product is shipped in insulated shippers and must be stored at 2 - 8°C (36 - 46°F) until use. A temperature log must be kept to document the refrigerator temperature. If the temperature is not maintained, Celldex should be contacted.

Varlilumab should be protected from light. However, sufficient light protection is provided by the secondary container (carton); no specific light protection is needed during preparation of the dosing solution and infusion.

Varlilumab is not formulated with a preservative. Therefore, once the sterile vials are entered (i.e., once varlilumab is drawn into a syringe), the drug should be used as soon as possible (typically within 3 hours if kept at room temperature or within 6 hours if refrigerated; or in accordance with any applicable institutional guidance).

Additional guidance regarding storage and handling of varlilumab will be provided within a pharmacy manual provided by Celldex.

5.2 Drug Preparation Vaccine Preparation

Only qualified personnel who are familiar with procedures that minimize undue exposure to them and to the environment should undertake the preparation, handling, and safe disposal of biotherapeutic agents. Designated members of the pharmacy staff (pharmacist and technicians) with appropriate training and experience will be designated as the study pharmacists and will prepare the vaccine. The pharmacists will be responsible for preparing the study medication for each patient. The pharmacist who is on duty on the day of the vaccine administration will be required to complete a Dosage Preparation Record to document the preparation process for each vaccine dose.

12 April 2020 Page 30 of 88 confidential

On the day of the scheduled vaccine, following the confirmation of clinical and lab data, one IMA950 vial [containing 578 μ g of each individual peptide (6.94 mg in total)] will be withdrawn from the freezer, dissolved in a total volume of 700 μ L of 4.2% sodium hydrogen carbonate solution containing EDTA (0.0025% w/v). One poly-ICLC vial (containing 2 mg drug in 1 ml) will be removed from the refrigerator and placed on the refrigerated cold pack. Both will be kept on ice prior to the mixing procedure described below. Before use, each vial should be gently swirled to ensure uniform mixing of the contents. Avoid excessive or vigorous agitation; do not shake.

Aseptic technique should be employed in the preparation of all study to prepare the mixture of IMA950 and poly-ICLC. Using a 3 ml syringe with a 21G needle, the pharmacist will first withdraw 0.7 ml (1.4 mg) poly-ICLC solution from the vial. Then, using the same syringe and needle, the pharmacist will withdraw 0.5 ml reconstituted IMA950 solution (out of total 0.7 ml in the vial). The pharmacist will then aspirate an additional 0.1 ml of air (approximate) from the empty part of the IMA950 vial. The pharmacist will then gently mix the solution in the syringe by gentle swirling and slow, repeated inversion of the syringe. Do not shake. The pharmacist will then pull back on the plunger to clear any vaccine mixture from the needle, remove the needle, expel any air from the syringe and affix with a plastic luer cap to the syringe. At this point, there should be 1.2 ml solution of mixed IMA950 and poly-ICLC in the 3 ml syringe. The prepared syringe should be labeled and then placed on a refrigerated cool-pack for transport and storage until administration. The vaccine should be administered within 2 hours following the completion of the mixing procedure.

Varlilumab Preparation

Varlilumab (CDX-1127) is formulated as a clear, colorless sterile solution intended for single-use parenteral administration. Each vial contains a nominal 5.0 mg/mL Varlilumab (CDX-1127) protein in a 10.0 mL volume of buffered solution composed of Sodium Phosphate, Potassium Phosphate, Potassium Chloride, Sodium Chloride, and Polysorbate 80 with a pH of 7.0. The varlilumab dose to be administered will be diluted to a final volume of 90 ml for infusion, according to the instructions provided by Celldex in the pharmacy manual. No dilution is necessary in cases where the drug volume is greater than 90 ml.

5.3 Drug Administration

Drugs included in the current regimen are: 1) IMA950, 2) Hiltonol (poly-ICLC), and 3) varlilumab (CDX-1127). Dose vials for each of these drugs will be made under GMP conditions for administration. Refer to the IND's CMC for additional production information (The IND # TBN [name], PhD). IMA950 and poly-ICLC will be administered as one formulation containing 4.96 mg total IMA950 peptides and 1.4 mg poly-ICLC subcutaneously (s.c.) at sub-inguinal sites (IMA950-poly-ICLC vaccine). CDX-1127 will be administered intravenously (i.v.) at 3 mg/kg. Each dose must be administered at the

12 April 2020 Page 31 of 88 confidential

clinical trial site by appropriately trained staff. The rationale for doses, schedule and the selected combination are discussed in the background and rationale section (Section 2).

Each dose of vaccine must be administered at the clinical trial site by appropriately trained staff. It will be administered as one formulation containing IMA950 [413 μg of each peptide per injected dose (4.96 mg in total)] and 1.4 mg poly-ICLC subcutaneously (S.C.) at sub inguinal sites.

It is recommended that the injections be given approximately 10 cm below the inguinal ligament, within an appropriately sterilized area of 3-5 cm in diameter located over the femoral artery, on the right thigh for all injections unless an induration from the previous vaccine prevents the injection on the same site. In this case, the injection site will be altered to the corresponding area on the left thigh. The date and time of the reaction will be documented on the Vaccination Toxicity Assessment Form and patients will be called 48 \pm 6 hours after injection to assess for local reaction.

Vaccine injections should not be given to areas of skin with dermatologic conditions (such as persistent injection site reactions, infection, edema, or scarring) that will not allow easy access for study drug administration or evaluation of localized adverse events. If such conditions or other circumstances contraindicate injections as outlined above for an individual patient, alternate sites can be used, but this should be discussed with the primary investigator.

Following each administration of vaccine, patients must remain in clinic for observation one hour to evaluate and treat any potential immediate hypersensitivity reactions.

Varlilumab (CDX-1127) should be administered as an IV. infusion (3 mg/kg) immediately following the SC. vaccine administration. Varlilumab should be administered as a 90-minute infusion using a volumetric pump with a 0.2 micron pore size, low-protein binding polyethersulfone (PES) membrane in-line filter. The infusion should be followed by a saline flush to clear the line. Varlilumab should not be administered as a bolus injection.

Following each administration, patients must remain in clinic for observation one hour to evaluate and treat any potential immediate hypersensitivity reactions.

Patients will be called 48 ± 6 hours after injection to assess for local reaction (see **Section 5.5.7** and **Appendix II**).

5.4 Screening

The screening procedures and assessments must be completed within 28 days or less of registration unless otherwise noted

- Informed consent
- Demographics
- Physical/neurological examination

12 April 2020 Page 32 of 88 confidential

- Vital signs
- Complete medical history
- KPS
- Review of concurrent medications
- MRI with and without contrast
- ECG
- UCSF pathology review for confirmation of WHO grade 2 glioma
- Complete blood count (CBC) with differential and platelet count
- Blood chemistry assessment, including:
 - Alkaline phosphatase, aspartate aminotransferase/alanine aminotransferase (ALT/AST), total bilirubin, calcium, blood urea nitrogen (BUN), creatinine, total protein, albumin, random glucose, potassium, sodium, chloride, bicarbonate
- Laboratory autoimmune assessment
 - Antinuclear antibody, thyroid-stimulating hormone (TSH), free thyroxine (FT4), rheumatoid factor
- Serum or urine pregnancy within 7 days prior to registration
- HBsAg, HBsAb and HBcAb for screening of active or chronic hepatitis B and C
- Urine analysis
- HLA typing prior to registration (must be positive for HLA-A2 based on flowcytometry or genotyping) *HLA typing can be done at any time prior to registration; 28 days or less of registration does not apply.

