- Uncontrolled intercurrent illness including, but not limited to ongoing or active
 infection (e.g. active or chronic hepatitis B and C), symptomatic congestive
 heart failure, unstable angina pectoris, or psychiatric illness/social situations that
 would limit compliance with study requirements

	 History or current status of immune system abnormalities such as hyperimmunity (e.g., autoimmune diseases) that needed to be treated by systemic therapy, such as immuno-suppressants and hypoimmunity (e.g., myelodysplatic disorders, marrow failures, AIDS, transplant immunosuppression). Receiving ongoing treatment with immunosuppressive drugs, or 		
	dexamethasone > 4mg		

Pilot randomized pre-surgical evaluation of varillumab on IMA950 vaccine plus poly-ICLC in patients with WHO grade II low-grade glioma

- 1) Arm 1: Patients will receive IMA950+poly-ICLC and CDX-1127
- 2) Arm 2: Patients will receive IMA950+poly-ICLC.

Drugs included in the current regimen are: 1) IMA950 peptides; 2) poly-ICLC and 3) CDX-1127. IMA950 and poly-ICLC will be administered as one formulation containing 4.96 mg total IMA950 peptides and 1.4 mg poly-ICLC subcutaneously (s.c.) at sub-inguinal sites. CDX-1127 will be administered intravenously (i.v.) at 3 mg/kg

Pre-surgical phase:

On days -23±2, -16±2, -9±2 and -2 relative to the scheduled surgery: All patients receive s.c. injections of IMA950/poly-ICLC vaccine. The 4th dose of pre-surgery IMA950/poly-ICLC vaccine must be administered between 24-48 hrs prior to scheduled surgery. PBMC sample (60-80 mL/draw) is obtained on the day of the 1st vaccine (on day -23±2); also at the D-23±2 visit, PK samples (1 x 10 cc red top tube/draw) will be collected prior to varlilumab administration and 30 minutes (±5 minutes) after the infusion has ended. For Arm 1 patients, Varlilumab (CDX-1127) will be administered i.v. on the day of the first vaccine immediately following the s.c. vaccination.

Surgery: The resected tumor tissue will be sent to the BTRC tumor bank.

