3.1 Inclusion Criteria

- **3.1.1** Patients must be ≥ 18 years old
- 3.1.2 Pathological criteria Patients must have a newly diagnosed or recurrent WHO grade II astrocytoma, oligoastrocytoma or oligodendriglioma that has been histologically confirmed by prior biopsy or surgical resection. If the pathological diagnosis was made outside of UCSF, the pathology must be reviewed and confirmed at UCSF.
- **3.1.3** Patients must be positive for HLA-A2 based on flow-cytometry or genotyping.
- **3.1.4** Before enrollment, patients must show non-enhancing T2-FLAIR lesions that are amenable to surgical resection. Surgical resection of at least 0.3 grams of tumor is expected to ensure adequate evaluation of the study endpoints.
- 3.1.5 Prior radiation therapy (RT) after initial diagnosis will be allowed but there must be at least 6 months from the completion of RT (or radiosurgery). Prior chemotherapy and any systemic molecularly targeted anti-tumor therapy will be allowed, and there must be at least 28 days from the last temodar chemotherapy, 42 days for nitrosourea; at least 14 days from the last dose for chemotherapy regimens given continuously or on a weekly basis with limited potential for delayed toxicity.

12 April 2020 Page 24 of 88 confidential

- **3.1.6** Karnofsky performance status (KPS) ≥ 70% (Appendix I)
- **3.1.7** Off or low dose (≤ 4 mg/day by Decadron) corticosteroid for at least for 2 weeks before the first pre-surgical vaccine
- 3.1.8 Adequate organ function within 28 days of study registration including:
 Adequate bone marrow reserve: absolute neutrophil (segmented and bands) count (ANC) ≥1.0 x 10⁹/L, absolute lymphocyte count (ANC) ≥4.0 x 10⁸/L, platelets ≥100 x 10⁹/L; hemoglobin ≥ 8 g/dL
 - Hepatic: Total bilirubin \leq 1.5 x upper limit of normal (ULN) for age and SGPT (ALT) \leq 2.5 x upper limit of normal (ULN) for age
 - Renal: Normal serum creatinine or creatinine clearance ≥60 ml/min/1.73 m²
- **3.1.9** Must be free of systemic infection. Subjects with active infections (whether or not they require antibiotic therapy) may be eligible after complete resolution of the infection. Subjects on antibiotic therapy must be off antibiotics for at least 7 days before beginning treatment.

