- 3.1.10 Women of child-bearing potential and men must agree to use adequate contraception (ex. Hormonal or barrier method of birth control or abstinence) prior to study entry and for the duration of study participation (until one month after the last vaccine) since the effects of the current regimen on the developing human fetus are unknown. Should a woman become pregnant or suspect she is pregnant while she or her partner is participating in this study, she should inform her treating physician immediately.
- **3.1.11** Patient must sign an informed consent document indicating that they are aware of the investigational nature of this study, which includes an authorization for the release of their protected health information
- 3.2 Exclusion Criteria
- 3.2.1 Presence of gliomatosis cerebri, cranial or spinal leptomeningeal metastatic disease
- **3.2.2** Presence of T1 Gadolinium (Gd) –enhancing lesions (on MRI) suggestive of high-grade glioma
- 3.2.3 Pathological diagnosis for the resected tumor demonstrates transformation to higher grade (i.e. WHO grade III or IV) gliomas. If a patient is diagnosed as HGG upon resection after receiving the pre-surgical treatment, the patient will be withdrawn from the study and considered for therapeutic options for HGG (trials for HGG or standard of care). The tumor tissue of such a case would be brought to the lab before the pathological diagnosis is made; and thus would be processed before the lab is informed of the final HGG diagnosis. Because HGG tissue may still reflect the

12 April 2020 Page 25 of 88 confidential

- vaccine effects, we will evaluate the tumor tissue to help us develop future approaches for HGG.^{75,76}
- 3.2.4 Pregnant women are excluded from this study because IMA950 and poly-ICLC are drugs with the potential for teratogenic or abortifacient effects. Because there is an unknown but potential risk for adverse events in nursing infants secondary to treatment of the mother with IMA950 plus poly-ICLC (IMA950-poly-ICLC hereafter) vaccine, breastfeeding should be discontinued if the mother is treated with IMA950-poly-ICLC vaccine.
- 3.2.5 Uncontrolled intercurrent illness including, but not limited to ongoing or active infection (including active/chronic hepatitis B and C), symptomatic congestive heart failure, unstable angina pectoris, or psychiatric illness/social situations that would limit compliance with study requirements

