- **3.2.6** History or current status of immune system abnormalities such as hyperimmunity (e.g., autoimmune diseases) that needed to be treated by systemic therapy, such as immuno-suppressants and hypoimmunity (e.g., myelodysplatic disorders, marrow failures, AIDS, transplant immunosuppression).
- **3.2.7** Any isolated laboratory abnormality suggestive of a serious autoimmune disease (e.g. hypothyroidism): Antinuclear antibody, thyroid-stimulating hormone (TSH), free thyroxine (FT4), rheumatoid factor
- **3.2.8** Any condition that could potentially alter immune function (AIDS, multiple sclerosis, diabetes, renal failure)
- **3.2.9** Ongoing treatment with immunosuppressive drugs or dexamethasone > 4mg
- **3.2.10** Use of any of the following concurrent treatment or medications:
 - radiation therapy
 - chemotherapy
 - interferon (e.g. Intron-A®)
 - allergy desensitization injections
 - growth factors (e.g. Procrit®, Aranesp®, Neulasta®)
 - Interleukins (e.g. Proleukin®)
 - any investigational therapeutic medication
- **3.2.11** Prior cancer diagnosis except the following:
 - squamous cell cancer of the skin without known metastasis
 - basal cell cancer of the skin without known metastasis
 - carcinoma in situ of the breast (DCIS or LCIS)
 - carcinoma in situ of the cervix

- 3.2.12 Any other acute or chronic medical or psychiatric condition or laboratory abnormality that could increase the risk associated with trial participation or trial drug administration or could interfere with the interpretation of trial results and, in the judgment of the investigator, would make the patient inappropriate for entry into the trial.
- **3.2.13** Participants with known addiction to any drugs

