5.6 Definition of Regimen Limiting Toxicities (RLT) and Suspension of Enrollment

5.6.1 Definition of RLT

Toxicity will be determined using the revised NCI Common Toxicity Criteria version 5.0 for Toxicity and Adverse Event Reporting (CTCAE) (http://ctep.info.nin.gov).

Management and dose modifications associated with the above adverse events are outlined in Section 5.7.

Participants will be observed for regimen limiting toxicity (RLT) throughout the study. The following are considered to be RLTs if they are judged possibly, probably or definitely associated with treatment. Should they occur, individual participants will be taken off study and no further injections will be given.

- Grade 2 or more any infusion reaction except for Grade 2 pain
- Grade 2 or more cytokine release syndrome
- Grade 2 or more bronchospasm or generalized uticaria (hypersensitivity)
- Grade 2 or more allergic reaction, such as exfoliative erythroderma, anaphylaxis, or vascular collapse
- Grade 2 or more autoimmune disease (e.g. hypothyroidism, autoimmune encephalitis)
- Any Grade 3 or more toxicity possibly, probably, or definitely related to the vaccine or Varlilumab with particular attention to the following events.

The following are also considered RLTs:

- Dosing delays > 6 weeks for IMA950+poly-ICLC vaccines or varillumab (Arm 1 patients only) administration.
- Delay of the scheduled surgical resection for longer than 2 weeks possibly, probably or definitely related to toxicity of the study treatment.

The following are NOT considered RLTs:

- Grade 3 nausea, vomiting, or diarrhea that resolves to ≤ grade 1 with or without treatment within 48 hours
- Grade 3 flu-like symptoms that resolve within 24 hours with the use of acetaminophen 650-1000 mg or with any NSAID

5.6.2 Events Which Will Temporarily Halt Enrollment at Any Time:

Certain events will be considered unacceptable and a single occurrence will lead to temporary closure of enrollment while under review for attribution to study therapy (not related to surgical procedures):

- The occurrence of grade 3 or 4 toxicity, excluding local skin reaction and flu-like symptoms in 3 patients
- Toxicity requiring the use of pressors, including grade 4 vascular leak syndrome or grade 3 and 4 hypotension
- Toxicity requiring ventilation support, including grade 4 respiratory toxicity

12 April 2020 Page 38 of 88 confidential

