Constitutional	Fever (in the absence of					
Symptoms	neutropenia)					
Constitutional	Dimara/Chilla					
Symptoms	Rigors/Chills					
Dermatology/Skin	Injection site reaction					

Rash

Metabolic/laboratory	Hepatic enzyme elevation
Pain	Pain - Muscle pain
Pain	Pain - Joint pain
Pain	Pain - Headache
Hematologic	Transient leucopenia (<1 week)

Grade 3:

CTCAE Category	Description
Hematologic	Leukopenia; Anemia
Constitutional	Fatigue (lethargy, malaise,
Symptoms	asthenia)
Neurology	Peritumoral Edema
Skin	Urticaria

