Any cases of suspected tumor progression or pseudo-tumor progression will be carefully reviewed by the study investigators to determine whether the subject should remain in the trial. In addition, pseudoprogression that necessitates intubation or pressors for >72 hours will be considered a regimen-limiting toxicity.

12 April 2020 Page 55 of 88 confidential

6 Study Parameters

Baseline evaluations will be conducted within 28 days prior to study enrollment. MRIs will be done \leq 28 days prior to the randomization. In the event that the patient's condition is deteriorating, laboratory evaluations will be repeated within 48 hours prior to initiation of the next vaccination.

If a vaccine is missed or a subject's treatment and/or testing days need to be rescheduled due to the subject's inability to comply with the study calendar (i.e., hospitalizations, business and vacation travel plans, illness, transportation issues, holidays, family emergencies, etc.), a window of ± one week is available for rescheduling of treatment and procedures per the discretion of the treating physician investigator, and as discussed with the principal investigator.

12 April 2020 Page 56 of 88 confidential

		Pre-surgical Post-Surgery Vaccin							accine	:S			Doot				
	Scre ening	D- 23 ±2 #1	D- 16 ±2 #2	D- 9 ±2 #3	D- ±2 #4	Sur ger y D0	Po st Op *	A 1 #1	A4 #2	A7 #3	A 10 #4	A 13 #5	A 16 #6	A 19 #7	A 22 #8	Wk A25	Post vac. Follo w- up ⁴
Informed Consent	Х																
Demographic	Х																
Tumor Tissue						Х											
HLA-A2	Х																
Randomizati on	Χ^																
Pathology Review	X ¹						Х										
IMA950+poly		Х	Х	Х	Х			Х	Х	X	X	Х	Х	Х	Х		
Varlilumab (Arm 1 only)		Х						Х		X		Х		X			
Complete Medical History	х																
Interval Medical History		Х	Х	Х	Х		х	Х	Х	Х	Х	Х	Х	Х	Х	Х	Х
Review of Concurrent Meds	Х	Х	х	Х	Х		Х	Х	Х	Х	Х	Х	Х	Х	Х	Х	Х
Physical Exam	Х	Х	Х	Х	Х		Х	Х	Х	Х	Х	Х	Х	Х	Х	Х	Х
Vital Signs#	Х	Х	Х	Х	Х		X	Х	Х	X	X	Х	Х	Х	Х	X	Х
Weight	X							Х								X	Х
Performance Status	Х	Х	Х	Х	Х		Х	Х	Х	Х	Х	Х	Х	Х	Х	Х	Х
Adverse Event Assessment		Х	x	x	Х		x	Х	Х	х	х	Х	Х	×	Х	х	Х
CBC w/diff plts	х	Х	Х	Х	Х		Х	Х	Х	Х	Х	Х	Х	Х	Х	Х	X ⁴
Serum chemistry ²	X	Х	X	Х	Х		Х	Х	Х	Х	Х	Х	Х	Х	X	X	X ⁴
Autoimmune assessment	Х																
HBsAg HBsAb HBcAb	Х															Х	
B-HCG	X																
Urynalysis ³	X															.,	
ECG ⁸	X					X ⁵	VA									X	
MRI Scans Research	Х					^~	X ⁶				X					Х	
Blood 8 x 10 cc green 1 x 5 cc red top		Х				x		Х				X		x		x	

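### Section 5.4 relies on three hepatitis B markers to screen for hepatitis C as well, and no hepatitis C test is specified, so undiagnosed hepatitis C would not be detected before dosing

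*Combined protocol and SAP*

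**What the plan says.** Section 3.2.5 excludes "Uncontrolled intercurrent illness including, but not limited to ongoing or active infection (including active/chronic hepatitis B and C", along with other conditions. The key exclusion criteria in the synopsis give the same example: "infection (e.g. active or chronic hepatitis B and C".

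The test meant to support this exclusion is in Section 5.4: "HBsAg, HBsAb and HBcAb for screening of active or chronic hepatitis B and C". The calendar in Section 6 has one viral hepatitis row, which reads "HBsAg HBsAb HBcAb". It is marked at screening and, as far as the extracted table can be read, again at Week A25.

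Three other provisions bear on the point:

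- Section 3.1.8 sets the ALT limit for entry at "2.5 x upper limit of normal (ULN) for age".
- Table 1 in Section 5.8.2 lists "Hepatic enzyme elevation" among the expected Grade 2 events of the vaccine.
- Section 3.2.12 lets the investigator exclude a patient with another condition that, "in the judgment of the investigator, would make the patient inappropriate for entry into the trial".

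**The concern.** HBsAg, HBsAb and HBcAb are the surface antigen, surface antibody and core antibody of hepatitis B. None of them detects hepatitis C. The sentence in Section 5.4 therefore states an intention to screen for two viruses and supplies tests for one. This is not a preference for wider screening, since the protocol itself says that hepatitis C is to be screened for.

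What is at stake is patient safety at entry. Someone with hepatitis C that nobody knows about could pass the specified screening and then receive a vaccine regimen expected to raise liver enzymes in some patients. If enzymes then rose, one possible cause would have gone unexamined before the first dose.

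**Working it through.** No arithmetic decides this point, and the plan gives no figure to reproduce. The check is to set every place that names hepatitis, or could catch it, beside what that place actually tests.

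| Place | Purpose or trigger | Hepatitis B test | Hepatitis C test |
|---|---|---|---|
| Synopsis, key exclusion criteria | Excludes B and C | none named | none named |
| Section 3.2.5 | Excludes B and C | none named | none named |
| Section 5.4 | Says it screens for B and C | HBsAg, HBsAb, HBcAb | none |
| Sections 5.5.1 to 5.5.6 and 5.5.8, visit lists | Treatment and follow-up | none | none |
| Section 6, calendar | Screening (and apparently Week A25) | HBsAg, HBsAb, HBcAb | none |
| Section 5.8.5, liver guidance | Work-up after liver tests rise on study | viral hepatitis in general | no assay named |

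Count of viral hepatitis markers specified: 3. Of these, 3 test for hepatitis B and 3 − 3 = 0 for hepatitis C.

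The next step is to ask whether another route would find hepatitis C before the first dose.

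1. Medical history (Section 5.4) and investigator judgement (Section 3.2.12) can pick up known infection. They cannot pick up infection that has not been diagnosed.
2. Screening ALT, AST and bilirubin may raise suspicion. They are non-specific, normal values do not rule out infection, and Section 3.1.8 admits ALT up to 2.5 times the upper limit of normal.
3. The liver guidance in Section 5.8.5 requires viral hepatitis to be considered when liver tests rise. That step comes after dosing has begun.

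No route closes the gap for undiagnosed hepatitis C before dosing.

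For the cost, Section 12.1.2 plans 15 patients per arm, so 2 × 15 = 30 evaluable patients if both arms complete. Sections 4.1 and 12.2 allow fewer, because the study may continue with Arm 2 only or stop early. Screen failures and the replacements allowed by Section 4.3 add to the number screened.

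**The case against.** The strongest reply accepts the omission and disputes its weight. Four parts of it deserve an answer.

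- **Toxicity counts.** A reader might infer that an unrecognised hepatitis C infection would distort the count of regimen limiting toxicities, and so the lead-in or stopping decisions. The documents do not support that. Section 5.6.1 already counts "Any Grade 3 or more toxicity possibly, probably, or definitely related to the vaccine or Varlilumab", and unknown hepatitis C status is unlikely to move a post-dose rise below possibly related. The Section 5.6.1 entry on dosing delays beyond 6 weeks carries no attribution condition. Under Section 5.7.1, an enzyme rise above 4 times baseline holds the vaccine, and failure to restart within 6 weeks means withdrawal for a regimen limiting toxicity, again with no attribution condition. This part of the reply stands.
- **Baseline liver status.** ALT, AST and bilirubin are measured at screening and at every vaccine visit, and Section 5.8.5 sets a separate trigger for patients whose baseline liver tests were abnormal. Baseline liver function is therefore known. What is missing is one possible cause of an abnormality. This narrows the point but does not remove it.
- **Eligibility.** A reader might infer that every patient with silent hepatitis C would be enrolled in breach of the criteria. Section 3.2.5 names hepatitis C as an example under uncontrolled intercurrent illness, and whether silent infection with acceptable liver tests falls under that heading is open to reading. A breach in each such case cannot be asserted. Even so, Section 5.4 says that the screening is meant to find hepatitis C.
- **Scale.** The documents give no prevalence, so neither a large nor a small number of affected patients can be claimed. This stands.

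**Conclusion.** The point holds as a screening error with a safety consequence. Section 5.4 is wrong as written: it names three tests for two viruses, none of the three detects hepatitis C, and nothing else in the protocol supplies the missing test. The specified tests would not detect undiagnosed hepatitis C before patients receive a regimen with expected hepatic enzyme elevation.

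The size is 0 of 3 markers. The number of patients affected is unknown. There is no claim that power, the primary immunological estimate or the toxicity counts would change. Nor is there a claim that known hepatitis C would be missed, since history and investigator judgement remain available.

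The conclusion rests on two things: the established meaning of the three markers, and the protocol text available here being complete for eligibility, screening and the calendar. If the site already runs a hepatitis C test under a laboratory manual or local practice, the gap is one of documentation, and Section 5.4 still needs correcting.

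**What to change.** Add a hepatitis C test to Section 5.4 and to the screening column of the Section 6 calendar. Anti-HCV with reflex HCV RNA is one option; the choice belongs to the sponsor's clinicians. In the same edit, state that HBsAg, HBsAb and HBcAb test for hepatitis B only. Leave their apparent Week A25 mark as it is, since this point gives no reason to alter it.

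The cost is one added assay per screened patient: about 30 evaluable patients if both arms complete, fewer if the trial stops or continues with Arm 2 only, and more with screen failures and replacements. Follow-up of any positive result and a minor protocol amendment come on top. Blood is already drawn at screening, so no extra visit is expected for patients who test negative. The documents give no screening blood volume, so whether an extra tube is needed cannot be said.
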